5.2. Scientific Rationale for Study Design

Despite a large safety database with a well-characterized safety profile and dose-response relationship of EPIDIOLEX in multiple indications, data on safety and efficacy of CBD remains limited in patients with PWS. However, as PWS is a rare disease with significant unmet needs, multiple large-scale studies would be impractical and may delay access to efficacious therapies.

Therefore, this study is designed as a seamless Phase 2/3 study to assess safety and tolerability of multiple candidate doses in Phase 2 of the study (10 to 40 mg/kg/day), followed by Phase 3 of the study. In Phase 3 of the study, 1 or 2 candidate dose level(s) will be recommended by the DMC for further development and assessment based on safety and tolerability data. This approach will allow a streamlined way to confirm the safety and tolerability profile of RAD011 in patients with PWS while limiting the number of patients exposed to lesser tolerated doses. In addition, data from patients who participated in Phase 2 of the study in the dose group(s) chosen for continued development and assessment in Phase 3 of the study will contribute to the overall intent-to-treat (ITT) population. This, in turn, allows for more efficient recruitment in this rare disease population.

The double-blind design will minimize patient and Investigator bias, whereas the placebo control will allow better delineation of efficacy and safety profiles of RAD011. The use of placebo groups in this study is acceptable as there are no FDA approved treatments for hyperphagia in patients with PWS. In addition, the IP will be administered in addition to standard of care therapy, which can include GH supplementation and any additional behavioral interventions that have been implemented and maintained stable throughout the study.

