5.8.4.1 Visit 5 (End of Screening, Beginning of Dose Escalation Period, Week 7)

The following assessments must be performed in person during Visit 5 (Week 7). All assessments must be performed prior to dosing on Visit 5, unless specified otherwise. Prior to assessing randomization eligibility, patients/caregivers must complete the HQ-CT.

- Review of concomitant medications
- Review of AEs
- Weight and height
- Vital signs, including BP, HR, temperature, RR, and oxygen saturation
- Complete physical examination
- Completion of the HQ-CT questionnaire (pre-dose)
 - The same caregiver should be available throughout the study to complete the questionnaires with the patient
 - HQ-CT must be completed prior to randomization

- Review of HQ-CT questionnaire scores and Inclusion/Exclusion criteria for eligibility
 - The EDC system will automatically calculate mean HQ-CT score from Visit 3, Visit 4 and Visit 5 inclusively. Patients with a mean HQ-CT score ≥ 13 will be eligible for randomization. Patients not eligible for randomization because of a HQ-CT score < 13 will not have the opportunity to participate in the long-term extension study (SCOUT-016)
 - The EDC system will also automatically calculate the change in HQ-CT score from Visit 2 (beginning of the Tolerability Period) to Visit 5 (end of the Tolerability Period/Beginning of Dose Escalation Period) inclusively. Patients must have a decrease in HQ-CT score ≤ 7 to be eligible for randomization and able to proceed to the Dose Escalation Period. Further details are defined in [Section 6.4](#)
 - Laboratory values collected prior to visit 5 should be used to assess eligibility
 - Patients meeting all inclusion and exclusion criteria should proceed to randomization.
 - Completion of the C-SSRS questionnaire (predose)
- Randomization
- Completion of the ABC, ESS-CHAD, CGI-S Hyperphagia, CaGI-S Hyperphagia, and Skin Picking questionnaires
- Resting 12-lead ECG in the supine position
- Collection of laboratory samples ([Section 10.1](#))
 - Urinalysis
 - Urine dipstick pregnancy test for females of childbearing potential only to be performed locally
 - Urine drug screen for drugs of abuse including THC
 - Chemistry panels (renal and liver function panels)
 - Hematology
 - Appetite hormones (including insulin, ghrelin, and leptin) Ghrelin samples will only be collected for Phase 3 patients at sites where proper collection is feasible.
- Pharmacokinetic sample ([Section 10.1.13](#))

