6.4.2. Tolerability Period

At the end of the Tolerability Period (Visit 5), Investigators will review a patient's eligibility to be randomized and proceed to the Dose Escalation Period.

Patients/caregivers must first complete the HQ-CT. The EDC system will automatically calculate a mean HQ-CT score from Visit 3, Visit 4 and Visit 5. Patients must have a mean HQ-CT score ≥ 13 to be eligible to be randomized and proceed to the Dose Escalation Period. Patients with a mean score < 13 will not be eligible for randomization and will not have the opportunity to participate in the long-term extension study (SCOUT-016).

In addition, the EDC system will also automatically calculate the change in HQ-CT score from the Tolerability Period to the Screening Period. This change is calculated as:

$$\text{Mean HQ-CT score (Visit 3, Visit 4, Visit 5)} - \text{Mean HQ-CT score (Visit 1, Visit 2)}$$

Patients with a decrease HQ-CT score ≤ 7 will be eligible for randomization. Patients with a decrease in HQ-CT score > 7 will not be eligible for randomization and unable to proceed to the Dose Escalation Period.

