11.1. Sample Size Determination

DMC Recommendation of Two RAD011 Doses

For the primary efficacy analysis, a total of 150 patients (50 patients per treatment group) aged 12 to 65 years will provide 90% power to compare each dose group vs. placebo with a two-sided alpha of 0.025. The study is powered to detect a difference in the HQ-CT from Baseline to Week 34 of 5 points with a standard deviation of 7 points. The 0.05 Type 1 error is split equally between groups (low dose and high dose). The low and high volume placebo groups will be combined for all comparisons to placebo. Assuming a 15% post-randomization dropout rate, approximately 180 patients (~60 patients per treatment group) will be evaluated for the primary efficacy analysis.

Thus, if the DMC recommends two RAD011 doses for Phase 3 of the study, approximately a total of 191 patients aged 12 to 65 years (approximate target of 200 patients) will be randomized in this study. The 191 reflects 176 patients required for primary efficacy analysis plus 15 patients randomized in the Phase 2 part of the study to the dose not selected for Phase 3 of the study.

Assuming a 20% pre-randomization eligibility failure rate (including HQ-CT eligibility criteria), approximately 240 patients will be enrolled into the Screening Period. An additional 10 patients per treatment group aged 8 to <12 years may be allowed to participate in Phase 3 of the study and will be randomized in a way to obtain a balanced number of patients on RAD011 (at dose levels recommended by the DMC) and placebo. Patients aged 8 to <12 will not be included in the primary efficacy analysis.

DMC Recommendation of One RAD011 Dose

For the primary efficacy analysis, a total of 100 patients (50 patients per treatment group) aged 12 to 65 years will provide 94% power to compare active vs. placebo with a two-sided alpha of 0.05. The study is powered to detect a difference in the HQ-CT from Baseline to Week 34 of 5 points with a standard deviation of 7 points. Assuming a 15% post-randomization dropout rate, approximately 118 patients (~59 patients per treatment group) will be evaluated for the primary efficacy analysis.

Thus, if the DMC recommends one RAD011 dose for Phase 3 of the study, approximately 148 patients aged 12 to 65 years (target approximately 150 patients) will be randomized in this study.

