11.4.2. Primary Endpoint

The primary endpoint, change in HQCT score from Baseline to End of Study (Week 34) will be analyzed for the mITT population based on the treatment policy estimand using a mixed model for repeated measures (MMRM) with change in HQCT score as the response variable and randomization assignment, Baseline HQ-CT score and stratification variables (age [≥ 16 or < 16 years] at randomization and GH treatment at randomization [yes/no]) and time \times treatment interaction as fixed effects. Patient will be included as a random effect with an unstructured covariance matrix. A multiple imputation will be used for missing data. Baseline will be defined as the mean HQ-CT score (Visit 1, Visit 2).

For the primary endpoint analysis at Week 34, multiple imputation will be used to assign a value to those cases with missing data. The full conditional specification method with predictive means matching as described in Berglund & Heeringa ([Berglund, 2014](#)) will be used. This method uses all of a patient's known primary outcome measures at Baseline, Weeks 10, 19, 27, and/or 34 weeks to impute any missing values for Week 34.

DMC Recommendation of two RAD011 Doses

The primary comparison will be mean change in HQ-CT as calculated via least square means comparing RAD011 low dose vs. placebo and RAD011 high dose vs. placebo at Week 34. Low dose and high dose groups will be compared to placebo at the two-sided 0.025 level so overall type 1 error is maintained at two-sided 0.05 level.

DMC Recommendation of one RAD011 Dose

The primary comparison will be mean change in HQ-CT as calculated via least square means comparing RAD011 vs. placebo at Week 34. RAD011 will be compared to placebo at the two-sided 0.05 level.

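### The Visit 3–5 HQ-CT mean, already computed before randomisation, is left out of the primary model and the imputation: a modest, avoidable loss of precision

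*Protocol*

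**What the plan says.** Section 11.4.2 of the protocol fixes the primary model. Change in HQ-CT is analysed by MMRM with treatment, Baseline HQ-CT, the age and growth-hormone strata, and time by treatment. On Baseline it says "Baseline will be defined as the mean HQ-CT score (Visit 1, Visit 2". It also fixes the inputs of the multiple imputation: the method uses each patient's "known primary outcome measures at Baseline, Weeks 10, 19, 27, and/or 34 weeks to impute any missing values for Week 34".

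Visits 1 and 2 both precede the six-week placebo Tolerability Period, since the Visit 2 questionnaire is completed before the first placebo dose (Section 5.8.3.1). Visits 3, 4 and 5 (Days 15, 29 and 43) follow. Section 6.4.2 has the EDC system "automatically calculate a mean HQ-CT score from Visit 3, Visit 4 and Visit 5", and that mean must be at least 13. It also enters the rule on the run-in decrease. Section 5.8.4.1 adds that the Visit 5 "HQ-CT must be completed prior to randomization". The protocol states no use of these three scores beyond eligibility and gives no reason for leaving them out of the analysis.

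Section 11.1 bases the sample size on "a difference in the HQ-CT from Baseline to Week 34 of 5 points with a standard deviation of 7 points", with 50 analysed patients per group.

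**The concern.** Every randomised patient has five pre-randomisation HQ-CT scores, and the primary analysis uses two. The three it drops are the later ones, taken on placebo and nearest in time to Week 34. Section 5.2 justifies the inactive period partly by the variability of HQ-CT responses, and that variability is also why a two-score mean is a noisy covariate.

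Leaving out a prognostic baseline variable does not bias a randomised comparison. It does leave avoidable residual variance, and so a wider confidence interval for RAD011 against placebo. Section 5.2 favours a design that "allows for more efficient recruitment in this rare disease population". Precision that needs no further patients serves the same purpose.

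**Working it through.** **1. The plan's own power.** Inputs from Sections 11.1 and 11.4.2: n = 50 per group, difference 5, SD 7. With two doses, "Low dose and high dose groups will be compared to placebo at the two-sided 0.025 level"; with one dose, "RAD011 will be compared to placebo at the two-sided 0.05 level".

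- SE = 7 × √(2/50) = 1.40; noncentrality = 5/1.40 = 3.57; 98 degrees of freedom.
- Noncentral t power: 0.900 at two-sided 0.025 and 0.943 at two-sided 0.05.

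Both stated figures (90% and 94%) reproduce.

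**2. Residual variance, equal correlation r between all visits (assumption).** With unit variance, the residual variance of the Week 34 score given the mean of k earlier scores is 1 − k·r²/(1 + (k−1)·r). The current plan has k = 2. Under equal correlation, using both means is equivalent to k = 5.

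| r | k = 2 | k = 5 | ratio | variance cut |
|---|---|---|---|---|
| 0.40 | 0.771 | 0.692 | 0.897 | 10% |
| 0.50 | 1 − 0.50/1.5 = 0.667 | 1 − 1.25/3 = 0.583 | 0.875 | 12.5% |
| 0.77 | 0.330 | 0.273 | 0.828 | 17% |

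**3. Correlation that decays with time (assumption).** The covariance is a stable part, a decaying part and noise. One example is 0.4 + 0.4 × 0.95^(weeks apart), plus noise 0.2, with scores at Weeks −2, 1, 3, 5, 7 and 34.

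- Variances of the Visit 1–2 and Visit 3–5 means: 0.872 and 0.833; covariance between them 0.704.
- Covariances with Week 34: 0.468 and 0.491.
- Residual variance given the Visit 1–2 mean: 1 − 0.468²/0.872 = 0.748. Given both means: 0.700. Ratio 0.936.

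Across decaying structures with a Visit 5 to Week 34 correlation of 0.21–0.56, the ratio is 0.917–0.977, a cut of 2–8%.

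**4. What the range means.** The SE scales with the square root of the ratio: √0.977 = 0.988 to √0.828 = 0.910, a fall of 1–9%. The equivalent sample size per arm is 50/0.977 = 51.2 to 50/0.828 = 60.4, so about 1 to 10 extra analysed patients.

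**5. Eligibility truncation.** Both means must be at least 13 and the decrease at most 7, which narrows the range of the covariates. Simulation with SD 7 and assumed means of 18 and 22 gives cuts of 1.5–16%. A second simulation (mean 19, a 2-point fall after Visit 2, SD 6–8, equal correlation 0.3–0.7) gives 4–12%.

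**6. Power at 50 per arm, difference 5, two-sided 0.025.** Section 11.1 does not say which SD the 7 is.

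| Reading of SD 7 | r = 0.5 | weakest decaying case | gain over all structures (points) |
|---|---|---|---|
| unadjusted Week 34 SD | 0.981 to 0.991 | 0.912 to 0.919 | 0–1.5 |
| SD of change from Baseline | 0.933 to 0.960 | 0.979 to 0.981 | 0.2–4.4 |
| residual SD after Visit 1–2 adjustment | 0.900 to 0.937 | 0.900 to 0.907 | 0.7–4.9 |

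**7. Slope by visit.** The correlation with the Visit 3–5 mean weakens over follow-up when it decays. In the decaying structures tested, one common slope across Weeks 10, 19, 27 and 34 cuts Week 34 variance by 0.2–8%; visit-specific slopes give 2–8%.

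**8. Missing Week 34 data.** This simulation used 59 per arm, correlation 0.55 and about 15% missing, with normal-regression imputation followed by ANCOVA as a simpler stand-in for the protocol's method. The empirical SE was 1.083 as planned, 1.076 with Visits 3–5 in the imputation only, and 1.039 with them in both. Bias was 0.00 under completely random missingness. In a deliberately adverse case, with missingness depending on the Visit 3–5 mean in opposite directions by arm, leaving it out moved the estimate by 0.16 point; including it in the imputation removed the shift. For a single patient whose Week 34 score is imputed from Baseline and Week 10 alone, the imputation variance falls by 1–11%. That is a patient-level figure, not the SE of the treatment effect.

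**The case against.** The strongest reply is that nothing in the protocol is wrong here. A baseline-adjusted MMRM with the stratification factors is a coherent choice, the comparison is unbiased and the power is as stated. The size of the gain rests wholly on assumed correlations. Equal correlation, which gives the larger figures, treats scores about 27 weeks apart as being as alike as scores two weeks apart. Under decay the SE falls by only 1–4%. With an SE of 1.40 and a 95% half-width of about 2.8 points, that is roughly 0.03 to 0.12 points on a 36-point scale. A single common slope may gain almost nothing. Section 11 leaves the handling of missing data to the SAP, which may add imputation variables, and imputation alone improves the SE by under 1%.

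Most of this stands, and it limits the point to a modest one. It does not remove it. Section 11.4.2 fixes the primary covariates and names the imputation inputs, so the omission is a choice made in this document. The change has almost no cost, and every structure examined shows some gain. Without the SAP one can say only that the protocol states no further use of these scores, and that is enough for the recommendation.

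**Conclusion.** The point holds as an efficiency improvement. The primary model and the listed imputation inputs omit a pre-randomisation HQ-CT mean that every randomised patient must have. The avoidable loss is about 2–17% of Week 34 residual variance (1.5–16% with eligibility truncation), or 1–9% of the SE. If correlation fades with time, the lower part of that range (2–8% of variance) is the more realistic. The range depends on assumed correlations, with no lasting run-in shift.

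No stated figure is wrong and the randomised comparison is not biased. With missing Week 34 data, that last statement also needs missingness not to depend, differently by arm, on Visit 3–5 scores beyond the variables already listed. Most of the gain comes from the model covariate; the imputation adds little precision but some protection on this point.

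**What to change.** Keep the Visit 1–2 Baseline and the definition of the endpoint. Before unblinding, amend Section 11.4.2 (and the SAP to match) to add the mean HQ-CT of Visits 3, 4 and 5 as:

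- a fixed covariate in the primary MMRM, preferably interacting with visit so that its slope can differ over follow-up; and
- a variable in the imputation model, so that the imputation contains every covariate the analysis uses.

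The cost is one degree of freedom with a common slope, or about four with a slope for each of Weeks 10, 19, 27 and 34, plus a sentence or two of text. It needs no extra visit, patient or data item, and the estimand is unchanged.

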The primary endpoint, change in HQ-CT score from Baseline to End of Study (Week 34), will be analyzed for the mITT population based on the treatment policy estimand using a mixed model for repeated measures (MMRM) with change in HQ-CT score as the response variable and randomization assignment, Baseline HQ-CT score and stratification variables (age [≥ 16 or <16 years] at randomization and GH treatment at randomization [yes/no]) and time \times treatment interaction as fixed effects. Patient will be included as a random effect with an unstructured covariance matrix. A multiple imputation will be used for missing data. Baseline will be defined as the mean HQ-CT score (Visit 1, Visit 2).

DMC Recommendation of two RAD011 Doses

The primary comparison will be mean change in HQ-CT as calculated via least square means comparing RAD011 low dose vs. placebo and RAD011 high dose vs. placebo at Week 34. Low dose and high dose groups will be compared to placebo at the two-sided 0.025 level so overall Type 1 error is maintained at two-sided 0.05 level.

DMC Recommendation of one RAD011 Dose

The primary comparison will be mean change in HQ-CT as calculated via least square means comparing RAD011 vs. placebo at Week 34. RAD011 will be compared to placebo at the two-sided 0.05 level.

Pharmacokinetic Analyses:

All PK analyses will be described in the pharmacokinetic analysis plan prior to performing statistical analyses. A pharmacodynamic analysis may be completed to evaluate exposure with efficacy and safety.

Safety Analyses:

The Safety Population will be used for all safety assessments. Safety assessments will be based on adverse events (AEs), Columbia-Suicide Severity Rating Scale (C-SSRS), vital signs, ECGs, and laboratory assessments. All analyses of safety will be described in the Statistical Analysis Plan (SAP).

All safety assessments will be descriptive, and no inferential statistics will be performed. All data listings will be provided for protocol specified safety data. The Medical Dictionary for Regulatory Activities will be used to classify all AEs with respect to System Organ Class (SOC) and preferred term. Adverse event summaries will include only treatment-emergent adverse events (TEAEs) by treatment group. Assessment of severity and relationship will also be presented. Adverse events leading to study discontinuation will also be summarized by SOC, Preferred Term, severity, and relationship.

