7.5. Randomization and Blinding

Randomization will occur at Visit 5 (Week 7) after review of all eligibility criteria by the Investigator.

Both Investigators and patients will be blinded to the randomization assigned treatment. During the Tolerability Period, all patients will receive 0.1 mL/kg/day of placebo. To maintain the blind, multiple placebo groups were created to mimic the RAD011 groups: low volume (0.1 mL/kg/day), mid volume (0.2 mL/kg/day), and high volume (0.4 mL/kg/day). During the dose escalation period, the volume of blinded therapy for the mid volume and high volume placebo groups will increase in the same manner as the mid dose and high dose RAD001 groups, further ensuring blinding between RAD011 and placebo.

The matching (appearance, smell and taste) placebo and RAD011 product will utilize the same MCT vehicle.

Phase 2 of the study

Patients who meet eligibility criteria will be randomized in a 2:2:2:1:1:1 manner to receive double-blind treatment with IP, defined as either low dose (10 mg/kg/day, [0.1 mL/kg/day])

RAD011, mid dose (20 mg/kg/day, [0.2 mL/kg/day]) RAD011, high dose (40 mg/kg/day [0.4 mL/kg/day]) RAD011, low volume (0.1 mL/kg/day) placebo, mid volume (0.2 mL/kg/day) placebo, or high volume (0.4 mL/kg/day) placebo using a centralized randomization system. Randomization will be stratified according to current use of GH treatment (yes/no) and age (≥ 16 or < 16 years old).

Phase 3 of the study

Following review by the DMC (Section 10.4), 1 or 2 dose levels will be recommended for continued development and assessment in Phase 3 of the study. Therefore, following the Tolerability Period, patients meeting randomization eligibility criteria will be randomized using a centralized randomization system in a way to obtain a balanced number of patients on RAD011 and placebo to receive double-blind treatment with IP at dose levels recommended by the DMC.

If 1 dose is recommended for continued development and assessment in Phase 3 of the study, randomization will be 1:1 (RAD011: placebo).

If 2 doses are recommended for continued development and assessment in the Phase 3 part of the study, randomization will be 2:2:1:1 (RAD011 dose 1: RAD011 dose 2: placebo: placebo).

Patients aged 8 to < 12 years may be allowed to participate in the Phase 3 part of the study and will be randomized in a way to obtain a balanced number of patients on RAD011 (at dose levels recommended by the DMC) and placebo.

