11.4.3. Secondary and Other Endpoints

All analyses of the secondary and other endpoints for continuous measures will be conducted analogous to the primary endpoint analysis, using, the baseline value of the relevant variable as a

covariate, and patient as a random effect. All analyses of the secondary and other endpoints will be described in the SAP.

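### If two doses go forward, a fixed 0.025 per dose is valid, but Holm gives more per-dose and both-dose power at the same overall 0.05 and the same N

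*Protocol*

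**What the plan says.** The point concerns only the branch in which the DMC recommends two doses (Section 10.4). With one dose, the full 0.05 is used.

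For two doses, Section 11.4.2 states: "Low dose and high dose groups will be compared to placebo at the two-sided 0.025 level so overall type 1 error is maintained". The Synopsis, under Efficacy Analyses, says the same. Section 11.1 and the sample-size part of the Synopsis add the equal split: "The 0.05 Type 1 error is split equally between groups (low dose and high dose"). None of these places has a step-down or a transfer of alpha after a success.

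The power statement is per comparison: "a total of 150 patients (50 patients per treatment group) aged 12 to 65 years will provide 90% power" for each dose against placebo at 0.025, for a "difference in the HQ-CT from Baseline to Week 34 of 5 points with a standard deviation of 7 points". No power is given for both doses succeeding, or for at least one. Placebo groups are pooled, and the 2:2:1:1 randomization in Section 7.5 becomes 1:1:1 after pooling.

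For the secondary endpoints, Section 11.4.3 says: "All analyses of the secondary and other endpoints will be described in the SAP". The primary testing rule is not deferred in that way; the protocol itself fixes it.

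**The concern.** A fixed equal split holds the second dose to 0.025 even after the first has succeeded. By then the first null hypothesis has been rejected, and the closed-testing argument behind Holm allows the other to be tested at the full 0.05 without raising family-wise error above 0.05. The protocol leaves that unused.

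What is at stake is the second dose's claim, not whether the trial finds any effective dose. A dose with p between 0.025 and 0.05 beside a successful dose is declared a failure solely because of the split. Section 5.2 justifies the seamless design by saying that in this disease "multiple large-scale studies would be impractical and may delay access to efficacious therapies". It does not speak of a second-dose claim, but the inference is fair that a dose lost this way would be hard to retest.

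**Working it through.** **Inputs** (Section 11.1 unless noted): difference 5 points, SD 7, 50 per arm, one pooled placebo group, two-sided 0.025 per dose. Equal arms follow from Section 7.5. A shared placebo with equal arms gives the two test statistics a correlation of 0.5.

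**1. The plan's own power.** The standardized effect is 5 / (7 × √(2/50)) = 5 / 1.4 = 3.571. The two-sided critical values are 2.241 at 0.025 and 1.960 at 0.05.

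- At 0.025: Φ(3.571 − 2.241) = 90.8% (noncentral t: 90.0%). The stated 90% reproduces.
- At 0.05, the one-dose branch: Φ(3.571 − 1.960) = 94.6% (noncentral t: 94.3%). The stated 94% reproduces.

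**2. Fixed split, both doses at 5 points** (bivariate normal, correlation 0.5).

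- Both succeed: P(Z1 > 2.241 and Z2 > 2.241) = 0.8452.
- At least one succeeds: 2 × 0.9082 − 0.8452 = 0.971.

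**3. Holm, same inputs.** The first step is the same 0.025 test, so power for at least one dose stays at 0.971.

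- Both succeed: 2 × P(Z1 > 2.241 and Z2 > 1.960) − P(both > 2.241) = 2 × 0.87404 − 0.8452 = 0.9029.
- Per dose: (0.9713 + 0.9029) / 2 = 0.9371.
- Trials in which the second dose's verdict changes: 0.9029 − 0.8452 = 0.0577, about 1 in 17.

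A simulation of 2,000,000 trials agrees within 0.001. With t-tests on 147 df, fixed split against Holm is 90.3% vs 93.4% per dose, 83.8% vs 89.8% for both, and 96.9% under either rule for at least one.

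**4. Other settings.** The 3- and 4-point effects are assumptions, not protocol figures.

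| True effects, n per arm | Quantity | Fixed split | Holm | At least one dose (either rule) |
|---|---|---|---|---|
| 5 and 5, n = 50 | per dose | 90.8% | 93.7% | 97.1% |
| | both | 84.5% | 90.3% | |
| 4 and 5, n = 50 | weaker dose | 73.1% | 80.4% | 94.3% |
| 3 and 5, n = 50 | weaker dose | 46.1% | 56.5% | 92.0% |
| 5 and 5, n = 59 | per dose | 94.9% | 96.8% | 98.8% |
| | both | 91.1% | 94.9% | |

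The n = 59 rows apply if none of the 59 randomized per arm (50 / 0.85) loses information.

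**5. Error rates.** With both doses null, family-wise error is 4.65% under either rule. With one dose null and the other at 5 points, the null dose is rejected in 2.5% of trials under the fixed split and 4.5% under Holm. The ceiling is 5.0%, reached in effect when the other dose is at 8 points.

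**6. Interaction with secondary endpoints.** The protocol states no gatekeeping rule, so this is an assumption: a dose's secondary endpoints are tested only after both primaries succeed under Holm, or after that dose's own primary succeeds under the fixed split. The stronger dose's secondary endpoints are then testable in 90.3% of trials (Holm) against 90.8% (fixed) at 5 and 5 points, but in 56% against 91% at 3 and 5.

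A middle course passes on half of the winner's alpha, so the other dose is tested at 0.025 + 0.0125 = 0.0375.

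- At 5 and 5 points it gives 92.6% per dose and 88.1% for both.
- At 3 and 5 it gives 52.0% for the weaker dose and 91.2% for the stronger.

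The winner's secondary endpoints are then tested at 0.0125 unless the other dose also succeeds. At 3 and 5, the weaker dose succeeds alone in 0.920 − 0.912 = 0.008 of trials, so both succeed in 0.520 − 0.008 = 0.512. The stronger dose therefore succeeds alone in 0.912 − 0.512 = 0.400, which is 0.400 / 0.912 = 44% of its successes.

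**The case against.** The best defence is that the current rule is a recognised, valid choice that delivers the only power the protocol promises. The Phase 3 objective asks for an effect of RAD011 on hyperphagia-related behavior. It sets no both-dose target, and the chance of finding at least one effective dose is the same either way. All of that is true, and it is why this is an efficiency point rather than a defect.

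Second, Holm dominates within the two primary tests but need not across the whole trial. Under a fixed split each dose can carry its own 0.025 to its own secondary endpoints, and full Holm with strict gatekeeping can badly delay the stronger dose's secondary claims. This stands as a reason to write the two rules together. It does not settle the matter for the fixed split, because the protocol commits no alpha to secondary endpoints. Half-passing softens the problem but, as shown above, often leaves those endpoints at 0.0125.

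Third, the gain may be smaller than at 50 per arm. The mITT population keeps anyone treated with one post-randomization HQ-CT, and missing Week 34 values are imputed, so the information may lie between 50 and 59 per arm. At 59 the gain is 1.9 points per dose and 3.8 for both. This narrows the size without removing it.

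Fourth, doses are chosen on safety and tolerability alone, so an ineffective dose could go forward, and its false-claim rate beside an effective dose would rise. It stays within the 0.05 the protocol already accepts overall.

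**Conclusion.** The concern holds as a point of lost efficiency. The fixed split is valid and correctly powered. Holm, at the same overall 0.05 and the same N, and with no dose ordering or correlation assumption, rejects everything the fixed split rejects and sometimes the second dose too.

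The gain at the protocol's inputs is 2.9 points per dose and 5.8 points for both doses, falling to 1.9 and 3.8 at 59 per arm. It is larger for the weaker dose if the doses differ in effect, by about 7 points at 4 and 5 and about 10 at 3 and 5. Power for at least one dose does not change.

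The figures assume equal arms, a common SD and normal test statistics; they do not model the MMRM or the multiple imputation. The point falls away if only one dose goes forward.

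**What to change.** Before database lock and unblinding (the deadline Section 11 sets for the SAP), replace the testing sentence in Section 11.4.2 and in the Synopsis under Efficacy Analyses with, for example:

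> The two dose–placebo comparisons will be tested by the Holm procedure at an overall two-sided 0.05: the smaller p-value at 0.025 and, if significant, the other at 0.05.

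In Section 11.1 and the matching Synopsis text, keep N and describe 90% per dose at 0.025 as a lower bound.

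Write this together with the SAP's rule for the secondary endpoints. If each dose's alpha is to pass to its own secondary endpoints, state what share goes to the other dose's primary test; half is one workable choice. If the sponsor prefers the fixed split for that reason, a sentence saying so is enough.

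The change costs no patients. It needs the text edits, the matching SAP wording and, if classed as a substantial amendment under Section 14.4, regulatory and IRB/IEC approval. The statistical price is the higher false-claim rate for a null dose beside an effective one, and simultaneous confidence intervals less direct than the 97.5% Bonferroni intervals.
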